## 6.8.2. Concomitant Antihyperglycemia Medication

Where appropriate, allowable non-insulin antihyperglycemic medication therapy may be obtained locally by the Lilly affiliate in the participating country from local commercial supplies and distributed to sites. It is acceptable for study participants to continue obtaining their noninsulin antihyperglycemic medications by the previous prescribing process. In the United States and Puerto Rico, a prescription card will be available for study participants to obtain their noninsulin antihyperglycemic medications with a prescription.

Dose adjustments of allowable non-insulin antihyperglycemic medications are permitted after randomization (during the treatment period) under the following circumstances and should be documented:

- situations that require short-term treatment interruption consistent with the product labeling for each respective country
- situations that require dose adjustment or discontinuation per country-specific label, for example, in the case of reduced eGFR
- in the case of increased hypoglycemia risk during the treatment period (as described in Section 8.3.3)
- a dose increases as part of rescue therapy, and
- for safety reasons at the discretion of the investigator.

## 6.8.3. Medications that Promote Weight Loss

Prescription or OTC medications that promote weight loss cannot be initiated after screening. If started after screening, these medications should be stopped immediately.

## 6.8.4. Systemic Glucocorticoids

Chronic systemic glucocorticoid therapy is allowed for no more than 14 consecutive days during the first 26 weeks, and during the periods from 26 to 52- weeks and 52 to 78- weeks.

This restriction does not apply to glucocorticoid therapy used as replacement therapy for adrenal insufficiency, or topical, intraocular, intranasal, inhaled preparations and intra-articular injections.

## 6.8.5. Treatment after the End of the Study

## 6.8.5.1. Treatment after Study Completion

Study interventions will not be made available to study participants after Visit 37 (Week 78) or after the participant's early discontinuation from study treatment.

At the last treatment visit (Visit 37 [Week 78] or ET visit), the investigator will prescribe a nonstudy basal insulin for use during the safety follow up period. Participants will continue their concomitant non-insulin antihyperglycemic medications at the discretion of the investigator and continue to monitor their FBG and complete the e-diary.

**Study Participants treated with LY3209590:** Study participants will receive the last injection of LY3209590 at Week 77 of the study and can begin the transition to the non-study insulin after Visit 37 (Week 78). At Visit 37 (Week 78), the investigator will review the instructions for transitioning to the non-study insulin. During this transition period, the participant's FBG should be used to guide dose initiation and adjustment for the insulin prescribed for the safety follow-up period.

No daily basal insulin will be required until the FBG is above 120 mg/dL (6.6 mmol/L) for 2 consecutive measurements. The prescribed non-study daily basal insulin should be started at a dose of 10 units/day and adjusted during the safety follow-up period based on FBG and according to the modified Riddle algorithm or investigator judgement in accordance with any country-specific label. Dose adjustments made for the non-study insulin during the safety follow-up period should be documented in the eCRF. An unscheduled visit in addition to Visit 801 may occur during this time to facilitate the transition to the non-study daily basal insulin.

Since LY3209590 has a half-life of approximately 17 days, a careful titration of the daily basal insulin is necessary to prevent hypoglycemia due to overlapping insulin action. Therefore, the investigator should consider titrating the daily insulin to reach 50% of the required daily dose at approximately 2-weeks and 80% at approximately 4-weeks.

**Study Participants treated with insulin degludec:** Study participants assigned to the insulin degludec treatment arm will transition to a non-study basal insulin after Visit 37 (Week 78). The investigator will prescribe the non-study insulin and titrate the dose based on their clinical judgement in accordance with the country-specific label for the basal insulin. The initial prescribed dose and any dose adjustments made during the safety follow-up period will be documented in the eCRF.

## 6.8.5.2. Emergency Situations and Special Circumstances

In emergency situations or special circumstances (for example, elective surgery, acute illness, and interrupted access to medicines), it may be necessary for study participants to change their dose of non-insulin antihyperglycemic medications and/or be treated with a non-study insulin. This will be allowed for up to 3 consecutive weeks for degludec or 3 consecutive doses for LY3209590 prior to Visit 22 (Week 26). After Week 26, dose changes to non-insulin antihyperglycemic medications or temporary treatment with a non-study insulin is allowed but must be documented by the investigator.

# 7. Discontinuation of Study Intervention and Participant Discontinuation/Withdrawal

Discontinuation of specific sites or of the study as a whole, are handled as part of Section 10.1, Appendix 1.

# 7.1. Discontinuation of Study Intervention

#### **Permanent Discontinuation of Study Intervention**

When necessary, a participant may be permanently discontinued from study intervention. If so, the participant may remain in the study and follow procedures for remaining study visits, as shown in the SoA.

A participant will be permanently discontinued from study intervention in the following situations:

- if the participant decides to stop study intervention
- if the participant becomes pregnant
- if participant has any significant study intervention-related hypersensitivity reaction
- if a participant is diagnosed with an active or untreated malignancy (except for successfully treated basal or squamous cell skin carcinoma)
- if the participant has not taken insulin degludec for more than 21 consecutive days or has missed more than 3 consecutive doses of LY3209590 during the period from randomization to Visit 22 (Week 26) unless the investigator has instructed the participant to temporarily stop treatment
  - if the investigator determines that the participant is persistently noncompliant after the 26-week treatment period
- if the investigator or sponsor decides that the study participant should be withdrawn from IP. If the decision is made because of a severe AE, an SAE, or a clinically significant laboratory value, the appropriate measures are to be collected and Lilly or its designee should be alerted

## Hypersensitivity reactions

If the investigator determines that a systemic hypersensitivity reaction has occurred related to study intervention administration, the participant may be **permanently discontinued** from the study intervention, and the Lilly-designated medical monitor should be notified.

If the investigator is uncertain about whether a systemic hypersensitivity reaction has occurred and whether discontinuation of study intervention is warranted, the investigator may consult the Lilly-designated medical monitor.

## 7.1.1. Liver Chemistry Stopping Criteria

The study drug should be interrupted or discontinued if one or more of these conditions occur:

Elevation from baseline	Exception
ALT or AST >8x ULN	
ALT or AST >5x ULN for more than 2 weeks	
ALT or AST >3x ULN and either TBL >2x ULN or	In participants with Gilbert's syndrome, doubling of
INR >1.5	direct bilirubin should be used for drug interruption/
	discontinuation decisions rather than TBL>2x ULN.
ALT or AST $>3x$ ULN with the appearance of fatigue,	
nausea, vomiting, right upper quadrant pain or	
tenderness, fever, rash, and/or eosinophilia (>5%)	
ALP $>3x$ ULN, when the source of increased ALP is	
the liver	
ALP >2.5x ULN and TBL >2x ULN	In participants with Gilbert's syndrome, doubling of
	direct bilirubin should be used for drug interruption/
	discontinuation decisions rather than TBL>2x ULN.
ALP >2.5x ULN with the appearance of fatigue,	
nausea, vomiting, right upper quadrant pain or	
tenderness, fever, rash, and/or eosinophilia (>5%)	
Source: FDA Guidance for Industry: Drug-Induced Live	r Injury: Premarketing Clinical Evaluation, July 2009,
and other consensus guidelines, with minor modification	S

Abbreviations: ALP = alkaline phosphatase; ALT= alanine aminotransaminase; AST = aspartate aminotransferase; FDA = Food and Drug Administration; INR = International normalized ratio; TBL = Total bilirubin level; ULN = Upper Limit of Normal

Resumption of the study drug can be considered only in consultation with the Lilly-designated medical monitor and only if the liver test results return to baseline and if a self-limited non-drug etiology is identified.

## 7.1.2. Temporary Interruption of Study Treatment

The investigator may interrupt study treatment, due to an AE, clinically significant laboratory value, hospital visits, travel, or shortage of study treatment supply. Refer to Section 6.8.5.2 for allowable intervals for temporary study treatment interruptions.

Every effort should be made by the investigator to maintain participants in the study and to restart study intervention promptly, as soon as it is safe to do so. Participants will continue their study visits and follow-up according to the SoA.

Participant should resume the dose prescribed before the temporary dosing interruption at the discretion of the investigator. Participant noncompliance should not be recorded as interruption of study intervention on the eCRF.

The dates of study intervention interruption and restart must be documented in source documents and entered on the eCRF.

Participants who have a temporary interruption of the study intervention will continue participating in the trial and continue study visits through the safety follow-up according to the protocol.

## 7.2. Participant Discontinuation/Withdrawal from the Study

Discontinuation is expected to be uncommon.

A participant may withdraw from the study

- at any time at the participant's own request
- at the request of the participant's designee (for example, parents or legal guardian)
- at the discretion of the investigator for safety, behavioral, compliance, or administrative reasons
- if enrolled in any other clinical study involving an investigational product, or enrolled in any other type of medical research judged not to be scientifically or medically compatible with this study
- if the participant, for any reason, requires treatment with a therapeutic agent that is prohibited by the protocol and has been demonstrated to be effective for treatment of the study indication. In this case, discontinuation from the study occurs prior to introduction of the new agent, and
- if a study participant is diagnosed with any type of diabetes mellitus other than T2D.

At the time of discontinuing from the study, if possible, the participant will complete procedures for an early discontinuation visit and post-treatment follow-up, if applicable, as shown in the SoA. If the participant has not already discontinued the study intervention, the participant will be permanently discontinued from the study intervention at the time of the decision to discontinue the study.

If the participant withdraws consent for disclosure of future information, the sponsor may retain and continue to use any data collected before such a withdrawal of consent. If a participant withdraws from the study, the participant may request destruction of any samples taken and not tested, and the investigator must document this in the site study records.

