### Primary Estimand (for primary objective)

### **US** registration

The *primary* clinical question of interest is: What is the treatment difference between LY3209590 and insulin degludec in change from baseline to Week 26 in HbA1c in the studyeligible participants with T2D currently on basal insulin regardless of treatment discontinuation for any reason and regardless of initiation of rescue medication?

The *treatment regimen estimand* will be used for the primary objective and is described by the following attributes:

• Treatment condition: randomized treatment regardless of treatment discontinuation and use of rescue medications

- Population: targeted study population (see Section 9.2 for details)
- Endpoint: change from baseline to Week 26 in HbA1c
- Remaining intercurrent events: none. The 2 intercurrent events, treatment discontinuation for any reason and initiation of rescue medication, are both addressed by the treatment condition of interest attribute
- Population-level summary: difference in mean changes between treatment conditions

Rationale for estimand: The treatment regimen estimand estimates how participants with T2D are treated in clinical practice and takes into account both efficacy and safety.

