## Visit 5 (Week 2) - Visit 37 (Week 78)

Participants assigned to LY3209590 will administer their weekly doses during the remaining treatment period. Non-insulin antihyperglycemic medications will be continued after randomization. Study participants must measure their FBG levels each day when possible or at a minimum 3 times per week. The participant's FBG will be used to titrate basal insulin dose adjustments throughout the study based on the study titration algorithm (Section 6.1.3). Blinded CGM will be worn by participants at designated weeks (SoA Section 1.3, Section 8.1.5.2). Concomitant Meds, AEs, including hypoglycemia events, required questionnaires, diary compliance, and other study procedures will be recorded and completed as outlined in the SoA. The last dose of LY3209590 will be administered in the week prior to Visit 37 (Week 78), and the last dose of insulin degludec will be administered a day prior to Visit 37 (Week 78). Comprehensive efficacy and safety evaluations will be conducted through the end of the treatment period.

Randomly assigned participants who are discontinued from IP before the end of the treatment period at Visit 37 (Week 78) are encouraged to remain in the study for continued monitoring. Both efficacy and safety data will be collected as indicated in the SoA after the early discontinuation of IP.

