## **Medical Conditions**

- 12. Have had a significant weight gain or loss in the past 3 months in the investigator's opinion (for example,  $\geq 5\%$ )
- 13. Have a diagnosis of T1D, latent autoimmune diabetes, or specific type of diabetes other than T2D (for example, monogenic diabetes, diseases of the exocrine pancreas, drug-induced or chemical-induced diabetes)
- 14. Are currently receiving or have received any time in the past 6 months, any of the following insulin therapies (outside of pregnancy) prior to screening, except for short-term treatment of acute conditions, and up to a maximum of 4 continuous weeks:
  - prandial insulin

- insulin mixtures
- inhaled insulin
- U-500 insulin, or
- continuous subcutaneous insulin infusion therapy

**Note:** Insulin use of any type or of any duration during a previous pregnancy is not considered an exclusion criterion.

- 15. Have received any of the following nonallowed diabetes medications within 90 days prior to screening: glinides, sulfonylureas, pramlintide, or thiazolidinediones
- 16. Have a history of greater than 1 episode of ketoacidosis or hyperosmolar state/coma requiring hospitalization in the 6 months prior to screening

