## 6.8. Concomitant Therapy

Study participants will be permitted to use concomitant medications that they require during the study, except excluded medications described in Section 5.2 (Exclusion Criteria) and the table below.

Investigative site staff will inform study participants that they must consult with the investigator or a designated site staff member when prescribed any new medications that may substantially affect glycemic values during the study, except when initiated for treatment of medical emergencies. Any additional medication initiated during the study (including OTC drugs, such as aspirin) must be documented in the CRF with the name of the drug and date(s) of administration. In addition, for permitted concomitant non-insulin antihyperglycemic medications, the dosage will also be documented and collected.

Non-study medications taken by study participants who are screened but not randomly assigned will not be reported to Lilly unless an SAE or AE occurs that the investigator believes may have been caused by a study procedure.

This table provides a summary of criteria for use of concomitant medications during the study.

Drug Class	Use during Screening/ Lead-In	Conditions for Use after Randomization			
		During Treatment Period	Acute Therapy	Rescue Therapy	During Safety Follow- Up Period
Drugs with approved weight loss indication a	Y	Y	Ν	N/A	N
Systemic glucocorticoid therapy b	Ν	Ν	Y°	N/A	N
Antihyperglycemia	Medications				
GLP-1 RAs	Y d	$Y^d$	N/A	Y	Y
DPP-4 inhibitors	$\mathbf{Y}^{\mathrm{d}}$	$\mathbf{Y}^{\mathrm{d}}$	N/A	Y	Y
SGLT2 inhibitors	$\mathbf{Y}^{\mathrm{d}}$	$\mathbf{Y}^{\mathrm{d}}$	N/A	Y	Y
Non-study basal insulins	Y d	(allowed only if study basal insulin is discontinued)	(allowed only if study basal insulin is temporarily discontinued)	See note	Y
Insulin mixtures	N	N	(allowed only if study basal insulin is discontinued)	See note	Y
Prandial insulin	Ν	Ν	Y	Y	Y
Meglitinides	Ν	Ν	N	Ν	Y
Alpha-glucosidase inhibitors	Y d	Y d	N/A	Y	Y
Sulfonylureas	Ν	Ν	N/A	Ν	Y
Thiazolidinediones	Ν	Ν	N/A	Ν	Y
Metformin e	Y d	Y d	N/A	Y f	Y

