1.2. Study Design

- Study BDCU is a Phase 3, multicenter, randomized, open-label, comparator-controlled study to evaluate the efficacy and safety of once-weekly basal insulin (LY3209590) compared to insulin degludec in participants with T2D treated with basal insulin.
- The study includes a 3-week screening/lead-in period, a 78-week treatment period, and a 5-week safety follow-up period.
- Participants will continue prior stable diabetes therapy with 0 to 3 allowed non-insulin antihyperglycemic medications during the study.
- Participants will discontinue their previous basal insulin doses at randomization and will be assigned to either LY3209590 or insulin degludec U100.
- Assignment to treatment groups will be determined by an interactive web-response system (IWRS). Participants will be randomly assigned to 1 of the 2 treatment groups in 2:1 ratio (LY3209590 : insulin degludec) at Week 0 (Visit 3). Stratification will be by country, HbA1c stratum at Week -3 (Visit 1) (<8.0%, ≥8.0%), and the type of basal insulin regimen at randomization (a. typical once-daily basal insulin; b. U-300 or BID regimens).
- This is a treat-to-target study, both treatment groups will undergo titration to achieve an FBG target within the range of 80-120 mg/dL. The primary endpoint at Week 26 (Visit 22) is based on participants reaching stable insulin dose by 8 to 12 weeks and glycemic stability in advance of the 26-week primary endpoint Hemoglobin A1c measure.
- Rescue therapy will be considered during the treatment period if the participants meet the protocol criteria of severe, persistent hyperglycemia.
- If study intervention is permanently discontinued, the participant will be encouraged to continue participation in the study for continued monitoring. Both efficacy (including HbA1c) and safety data will continue to be collected per the schedule of activities in the protocol.

2. Statistical Hypotheses

Primary Hypothesis

The primary objective of this study is to test the hypothesis that LY3209590 is noninferior to insulin degludec on glycemic control as measured by change from baseline to Week 26 (Visit 22) in HbA1c in participants with T2D currently on basal insulin. Thus, the null hypothesis (H_{01}) to be tested is the difference in the change from baseline to Week 26 (Visit 22) in HbA1c (LY3209590 – insulin degludec) is greater than the noninferiority margin (NIM). The 2-sided 95% confidence interval (CI) will be used for testing the noninferiority.

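### Section 7.2 takes participants out of the study before a prohibited glucose-lowering agent is started, although the US primary estimand needs their Week 26 HbA1c

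*Protocol*

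**What the plan says.** Protocol Section 7.2 lists reasons for leaving the study. One is that the participant needs a protocol-prohibited agent with demonstrated efficacy in the study indication. That bullet continues: "In this case, discontinuation from the study occurs prior to introduction of the new agent". For anyone leaving who is still on study insulin, the section adds that "the participant will be permanently discontinued from the study intervention at the time of the decision to discontinue the study".

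What counts as prohibited comes from Section 6.8, which permits concomitant medication "except excluded medications described in Section 5.2 (Exclusion Criteria) and the table below". Exclusion criterion 15 names "nonallowed diabetes medications within 90 days prior to screening: glinides, sulfonylureas, pramlintide, or thiazolidinediones". The Section 6.8 table marks sulfonylureas, thiazolidinediones and meglitinides as not allowed, both during treatment and as rescue.

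The US primary estimand (Protocol Section 3) sets the treatment condition as "randomized treatment regardless of treatment discontinuation and use of rescue medications". Other parts of the plan keep people in follow-up once study insulin stops:

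- Protocol 4.1.1: participants who stop study drug early "are encouraged to remain in the study for continued monitoring", with efficacy data still collected.
- Protocol 7.1: after permanent discontinuation of study drug "the participant may remain in the study and follow procedures for remaining study visits".
- SAP 1.2: "If study intervention is permanently discontinued, the participant will be encouraged to continue participation in the study for continued monitoring", and HbA1c is named among the data still collected.
- Protocol 6.8.1: someone who needs a non-study basal insulin or a mixture as rescue stops study insulin but stays in the study for the remaining visits.

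**The concern.** The estimand and the withdrawal rule pull in different directions. A treatment-policy estimand is only as good as follow-up after the intercurrent event. Section 7.2 ends follow-up in people whose glucose control, or tolerance of the permitted options, has led to a new agent. The estimand gives no reason to follow a participant rescued with a non-study basal insulin but not one given a sulfonylurea. The documents offer no reason specific to this bullet.

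The Schedule of Activities collects HbA1c at the early termination visit, but that value does not fill the gap. For the treatment regimen estimand, the observation table in SAP 4.1 admits planned Week 26 measurements, or unplanned ones on that same visit day. Anyone who leaves earlier is therefore imputed under SAP 4.3.2.

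The rule also thins the group that the imputation learns from. Because Section 7.2 stops study insulin, a participant kept in follow-up could have been a retrieved dropout. Treatment-regimen time in range at Week 26 (SAP 4.4.1.2) and HbA1c at Weeks 52 and 78 (SAP 4.4.2.1) lose data in the same way.

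**Working it through.** **Who is caught.** In the rescue column of the Section 6.8 table, GLP-1 receptor agonists, DPP-4 inhibitors, SGLT2 inhibitors, alpha-glucosidase inhibitors, metformin and prandial insulin are allowed. Non-study basal insulin and mixtures are allowed once study insulin stops. That leaves sulfonylureas, thiazolidinediones and meglitinides, plus pramlintide through exclusion criterion 15. So Section 7.2 does not literally contradict 6.8.1; the two cover different agents.

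**Is the event inside the estimand?** Starting one of these agents is not rescue as the protocol defines it, and it is not a named intercurrent event. But Section 7.2 also stops study insulin, and Protocol Section 3 covers treatment discontinuation for any reason. The Week 26 value is therefore wanted.

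**Plan's own figures.** Inputs from Protocol 9.5: 939 randomized 2:1 (626 and 313), 15% dropout, SD 1.1, true difference 0, 2-sided 95% CI.

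- Completers: 626 × 0.85 = 532.1 and 313 × 0.85 = 266.05, total 798.
- SE = 1.1 × √(1/532 + 1/266) = 0.0826.
- Power = Φ(margin/SE − 1.96). Margin 0.3: Φ(3.63 − 1.96) = 95.3%. Margin 0.4: 99.8%.

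Both match the stated at least 95% and greater than 99%.

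**Values lost before Week 26.** The documents give no frequency, so the shares are assumed. The power column takes the losses as additional to the 15% dropout.

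| Assumed share | LY3209590 (of 626) | Degludec (of 313) | SE | Power, margin 0.3 |
|---|---|---|---|---|
| 0.5% | 3.1 | 1.6 | 0.0828 | 95.2% |
| 1% | 6.3 | 3.1 | 0.0831 | 95.1% |
| 2% | 12.5 | 6.3 | 0.0836 | 94.8% |

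Power at the 0.4 margin stays at 99.8% throughout.

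**Shift in an arm mean.** Shift = share lost × (imputed minus actual Week 26 HbA1c). With an assumed error of 0.5 to 1.0 points:

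- Low end: 0.005 × 0.5 = 0.0025 points, or 0.8% of the 0.3 margin.
- High end: 0.02 × 1.0 = 0.02 points, or 6.7% of the 0.3 margin.

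If only one arm is affected, the treatment difference moves by the same amount. Equal shares with equal errors cancel. A harsher assumption, 5% versus 1% lost with a 1.0-point error, gives (0.05 − 0.01) × 1.0 = 0.04 points, or 13% of the 0.3 margin.

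**Retrieved-dropout threshold.** SAP 4.3.2 switches to return-to-baseline imputation if either arm has fewer than 8 retrieved dropouts. The 313-person degludec arm is the more exposed. As an illustration with assumed rates, take the number retrieved in that arm as binomial with n = 313:

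- 3% retrieved (mean 9.4): chance of fewer than 8 is 28%.
- 3.5% retrieved: 14%.
- 4% retrieved (mean 12.5): 6.5%.

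Near the threshold, keeping another 0.5% to 1% of an arm (about 2 to 3 people) can decide which imputation method is used.

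**The case against.** The strongest reply is that the list in Section 7.2 opens permissively, with the verb may. A site could read the disputed sentence as fixing only the order of events once withdrawal has been chosen, with Sections 4.1.1 and 7.1 still allowing follow-up. That reading is available, but the sentence itself is directive and no other passage exempts these participants. If sites read it differently, retention will vary by site in an open-label trial, which is a reason to clarify it.

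The second reply is that the rule will rarely apply. So many rescue routes are open that few people will require one of the remaining classes before Week 26, and Section 7.2 itself expects discontinuation to be uncommon. This stands, and it limits the size of the point. It is also fair that these cases may fall inside the 15% dropout allowance, in which case planned power is not reduced at all.

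Third, the SAP anticipates missing Week 26 values. Section 4.3.2 imputes them, and Section 4.3.3 adds a two-way tipping-point analysis and imputation under the noninferiority null. Those analyses show how far a conclusion depends on missing data. They do not recover values that could have been collected.

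That the missingness is informative is plausible from the reason for leaving, but the documents do not demonstrate it.

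**Conclusion.** The concern holds as a misalignment between the withdrawal rule and the US treatment regimen estimand. As worded, the rule produces missing Week 26 HbA1c that ordinary follow-up would have supplied.

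The numerical effect is small: at most about 0.02 HbA1c points in an arm mean, and at most about half a percentage point of power at the 0.3 margin. Those figures rest on an assumed 0.5% to 2% leaving under this rule before Week 26, and an assumed imputation error of 0.5 to 1.0 points. The noninferiority conclusion is unlikely to depend on it. The efficacy estimand is little affected, because its data already stop at study-drug discontinuation or rescue.

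The change is worth making because the missing data are avoidable and the remedy is cheap.

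**What to change.** In the Section 7.2 bullet, replace discontinuation from the study with permanent discontinuation of study intervention where required. Alternatively, move the rule to Section 7.1, where it fits better. State that the participant continues scheduled visits and HbA1c collection per the Schedule of Activities, following the wording of Section 6.8.1 for non-study basal insulin and mixtures. Have the site record the new agent and its start date; Section 6.8 already requires the name and dates of any added medication. Leaving the study remains possible at the participant's request or for the other listed reasons.

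The cost is one sentence of protocol text, with the ethics review that Section 10.1.1 requires for any amendment. It adds no visits or procedures, since these participants would complete visits already scheduled.
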